1.2 Schema

Figure 1-1: Study schematic

IGA= Investigator’s Global Assessment; IMP=investigational medicinal product; MAP=managed access program; PASI=Psoriasis Area and Severity Index; PEOT=Premature End of Treatment; Q4W=every 4 weeks; SFU=Safety Follow-Up; W=Week

^a If a participant completes Week16 and is provided the continued treatment with bimekizumab as part of the MAP, SFU is not required.

1.3 Schedule of activities

Table 1-1: Schedule of study assessments

Protocol activity	Visit ^a / Week	Treatment Period							SFU ^c
		Screening ^b	Baseline (W0)	W1	W2	W4	W8	W12	
Informed consent	X								
Inclusion/exclusion	X	X							
Urine drug screen	X								
Demographic data	X								
PSO history	X								
Significant past medical history and concomitant diseases	X	X ^d							
Physical examination ^{e, f}	X	X					X	X	X
Height		X							
Body weight		X						X	
Vital signs ^g	X	X	X	X	X	X	X	X	X
Hematology and biochemistry	X	X	X	X	X		X	X	X
Urinalysis	X	X						X	X
ECG	X							X	
Pregnancy testing ^h	X	X			X	X	X	X	X
Hepatitis B and C testing ⁱ	X								
HIV testing ^j	X								
Chest x-ray ^k	X								

Table 1-1: Schedule of study assessments

Protocol activity	Visit ^a / Week	Treatment Period							SFU ^c	
		Screening ^b	Baseline (W0)	W1	W2	W4	W8	W12		W16/ PEOT
IGRA TB test		X								
TB questionnaire ^l		X	X					X ^l		X
PASI		X	X	X	X	X	X	X	X	X
IGA		X	X	X	X	X	X	X	X	X
Scalp IGA ^m			X		X	X	X	X	X	X
Percentage of BSA		X	X	X	X	X	X	X	X	X
DLQI			X		X	X	X	X	X	
PHQ-9		X	X			X	X	X	X	X
C-SSRS		X	X			X	X	X	X	X
PSD (P-SIM) (daily)		X	X	X	X	X	X	X	X	
Concomitant medication		X	X	X	X	X	X	X	X	X
AEs		X	X	X	X	X	X	X	X	X
IRT ^{n, o}		X	X	X	X	X	X	X	X	X
Blood sample for PK plasma BKZ concentrations and anti-BKZ antibodies ^p			X			X	X	X	X	X
BKZ or placebo administration ^{n, o}			X			X	X	X		

AEs=adverse events; BKZ=bimekizumab; BSA=body surface area; DLQI=Dermatology Life Quality Index; ECG=electrocardiogram; eCRF=electronic Case Report Form; C-SSRS=Columbia Suicide Severity Rating Scale; HBcAb+=positive for anti-hepatitis B core antibody; HBsAg+=positive for hepatitis B surface antigen; HCV=hepatitis C virus; HIV=human immunodeficiency virus; IGA=Investigator’s Global Assessment; IGRA=interferon-gamma release assay; IMP=investigational medicinal product; IRT=interactive response technology; MAP=Managed Access Program; PASI=Psoriasis Area Severity Index; PEOT=Premature End of Treatment; PHQ-9=Patient Health Questionnaire-9; PK=pharmacokinetic; PSD=patient symptom diary; P-SIM=Patient Symptom and Impact Measure; PSO=psoriasis; SFU=Safety Follow-Up; TB=tuberculosis; W=Week

- ^a Visit windows of ± 3 days from the first dose (W0) to the Week 16 visit. The SFU Visit window is ± 7 days from last dose.
- ^b The Screening Period will last 2 weeks, but can be extended up to a total of 5 weeks in cases where a laboratory assessment needs to be repeated or to allow washout of prohibited medications.
- ^c For study participants not entering the MAP, the SFU Visit will occur 20 weeks after the final dose of IMP. No SFU will occur for study participants entering the MAP.
- ^d Ensure no significant changes in medical history.
- ^e Includes evaluation of signs and symptoms of active TB and risk for exposure to TB.
- ^f The physical examination will be performed as per protocol.
- ^g Vital signs (sitting systolic and diastolic blood pressure, pulse rate, and body temperature) are to be measured prior to blood sampling, and prior to IMP dosing, where applicable.
- ^h Pregnancy testing will consist of serum testing at Screening. A urine pregnancy test will be administered at all other visits.
- ⁱ Study participants who have evidence of or test positive for hepatitis B by any of the following criteria: 1) HBsAg+; 2) HBcAb+ are excluded. A positive test for HCV is defined as: 1) positive for hepatitis C antibody (anti-HCV Ab), and 2) positive via a confirmatory test for HCV (for example, HCV polymerase chain reaction) are also excluded. Study participants will also be tested for antihepatitis B surface antibody.
- ^j The HIV test results will not be recorded in the eCRF.
- ^k Screening chest x-ray must occur within 3 months prior to the Screening Visit.
- ^l Tuberculosis questionnaire will be required at PEOT.
- ^m The scalp IGA will only be assessed for those study participants with scalp involvement (scalp IGA score >0) at Baseline.
- ⁿ IMP administration is based on randomization.
- ^o The dosing window is ± 3 days relative to the scheduled dosing visit through Week 16.
- ^p Samples will be collected prior to any IMP dosing at a visit.
- ^q If an Unscheduled Visit is conducted due to safety or efficacy reasons, a C-SSRS assessment will be performed with the subject during the visit. If an Unscheduled Visit is conducted for reasons other than safety or efficacy concerns (eg, repeated collection of a laboratory specimen due to collection or analysis issues), a C-SSRS will not be required at these visits.

2 INTRODUCTION

2.1 Study rationale

Psoriasis is a common, chronic inflammatory disease characterized by a series of linked cellular changes in the skin: hyperplasia of epidermal keratinocytes, vascular hyperplasia and ectasia, and infiltration of T lymphocytes, neutrophils, and other types of leukocytes in affected skin. Therapy for patients with PSO varies according to the severity of disease. Limited or mild disease is often treated with topical therapies such as corticosteroids and vitamin D analogs. Patients with more severe disease are often treated with phototherapy, methotrexate, cyclosporine, the oral phosphodiesterase 4 inhibitor apremilast, or biologic agents, such as tumor necrosis factor (TNF) antagonists, interleukin (IL)-12/23 inhibitors, IL-23p19 inhibitors, and IL-17A inhibitors.

Though the pathophysiology of PSO is not fully understood, the importance of T-cells and inflammatory cytokines has been demonstrated by the clinical benefit provided by therapies directed at these targets (Krueger and Ellis, 2005). While antibodies targeting IL-17A cytokines have demonstrated efficacy in patients with PSO, psoriatic arthritis (PsA), and ankylosing spondylitis, as yet, no approved therapeutic approach selectively and potently inhibits the activity of both IL-17A and IL-17F (Krueger and Ellis, 2005).

Bimekizumab is a humanized, full-length monoclonal antibody (mAb) of the immunoglobulin G1 (IgG1) subclass with 2 identical antigen binding regions that potently and selectively bind and neutralize IL-17A, IL-17F, and IL-17AF cytokines. This property makes bimekizumab distinct from other IL-17-targeting agents, like secukinumab and ixekizumab (selective anti-IL-17A cytokine-targeting mAbs) or brodalumab (an-IL-17 receptor-targeting mAb). Bimekizumab is being developed for the treatment of adults with moderate to severe plaque PSO. Parallel programs in the inflammatory diseases of PsA, axial spondyloarthritis, and hidradenitis suppurativa are ongoing.

The purpose of this study is to evaluate the efficacy and safety of bimekizumab in adult Korean study participants with moderate to severe plaque PSO. Following the completion of the pivotal global Phase 3 program of bimekizumab in moderate to severe PSO, the aim of this study is to bridge the existing evidence of efficacy and safety of bimekizumab from the Phase 3 program with limited Korean participation to a Korean population of study participants with moderate to severe PSO.

2.2 Background

Psoriasis is a common, chronic inflammatory disease characterized by inflammation and keratinocyte proliferation. Plaque PSO, the most common form of the disease, is typified by areas of red, inflamed skin, often covered with thick, micaceous, silver-colored scales on extensor surfaces. Plaques may be pruritic and painful as the skin cracks and bleeds. In severe cases, plaques grow and merge into one another, covering large areas.

In addition to the impact on skin, PSO has a multitude of psychosocial and emotional effects on patients, including increased self-consciousness, frustration, fatigue, depression, and suicidal ideation. As a result, patients frequently report sleeping problems, difficulties at work, problems interacting with family members, disrupted leisure activities, and sexual difficulties

(Dowlatshahi et al, 2014; Gottlieb, 2005; Mukhtar et al, 2004; Ortonne, 2004; Krueger et al, 2001).

A number of comorbidities have been associated with PSO, especially with more severe PSO. Psoriatic arthritis, cardiovascular (CV) disease, metabolic syndrome, chronic pulmonary disease, peptic ulcer disease, renal disease, and diabetes have all been demonstrated to have an increased prevalence in PSO patients (Yeung et al, 2013; Christophers et al, 2010; Gisondi et al, 2007; Gelfand et al, 2006).

The reported prevalence of PSO in countries ranges between 0.09% and 11.43%, with at least 100 million individuals affected worldwide (WHO report on psoriasis, 2016). There are a variety of forms of PSO, including plaque, guttate, inverse, pustular, and erythrodermic. Plaque PSO (PSO vulgaris) is the most common, comprising approximately 80% to 90% of all cases. It is estimated that approximately 80% of patients with plaque PSO have mild to moderate disease, while 20% of patients have more severe disease, which affects either greater than 5% of BSA or is located on high impact areas including the scalp, genitals, hands, and nails (Boehncke and Schön, 2015; Menter et al, 2008).

Descriptions of nonclinical and clinical bimekizumab data, including the status of ongoing studies, are provided in the current version of the Investigator's Brochure (IB).

2.3 Benefit/risk assessment

Based on the limited data collected from Korean study participants in the completed Phase 3 pivotal program, the benefits and risks of bimekizumab administration in adult Korean study participants are expected to be similar to results in adult study participants with PSO to date.

In studies of bimekizumab in moderate to severe PSO, study participants achieved and maintained skin clearance across multiple efficacy variables, as assessed by PASI (change from Baseline and by various levels of response) and IGA responses, after up to 56 weeks of bimekizumab 320mg sc treatment administered Q4W or Q4W for an initial 16 weeks followed by every 8 weeks (Q8W) maintenance treatment. The observed safety data were as expected considering the mechanism of action of bimekizumab and the population under investigation. The vast majority of AEs were nonserious, mild to moderate, and did not lead to IMP discontinuation. The most commonly reported TEAEs in bimekizumab-treated study participants were nasopharyngitis, oral candidiasis, and upper respiratory tract infection.

Prespecified safety topics of interest for the study are: infections (serious, opportunistic, fungal, and TB), neutropenia, hypersensitivity, suicidal ideation and behavior, major CV events, liver function test (LFT) changes/enzyme elevations, malignancies, and inflammatory bowel diseases (IBD). This is based on findings from the bimekizumab clinical program to date, potential risks generally associated with biologic immunomodulators, or findings from other medicines with a related mechanism of action. There are no specific AE reporting requirements for these topics, however special monitoring, additional data collection activities, and/or enhanced signal detection activities (within UCB) are in place.

More detailed information about the known and expected benefits and risks and reasonably expected AEs of bimekizumab may be found in the IB.

3 OBJECTIVES AND ENDPOINTS

Objectives	Endpoints
Primary	Co-Primary Endpoints
To evaluate the efficacy of bimekizumab compared with placebo	
Co-Primary Endpoint 1:
 
 Participant-level outcome: PASI90 response at Week 16 
Co-Primary Endpoint 2:
 
 Participant-level outcome: IGA 0/1 (clear or almost clear with at least a 2-category improvement from Baseline) response at Week 16
Secondary	
To evaluate the efficacy of bimekizumab compared with placebo at achieving complete skin clearance (PASI100/IGA 0)	
 Participant-level outcome: PASI100 response at Week 16 Participant-level outcome: IGA 0 (clear with at least a 2-category improvement from Baseline) response at Week 16
To evaluate the efficacy of bimekizumab compared with placebo at achieving rapid response (PASI75)	
 Participant-level outcome: PASI75 response at Week 4
To evaluate the efficacy of bimekizumab compared with placebo on itch, pain, and scaling	
Reported by study participants using the PSD (also published as P-SIM [Gottlieb et al, 2020]):
 
 Participant-level outcome: PSD (P-SIM) response for itch at Week 16 Participant-level outcome: PSD (P-SIM) response for pain at Week 16 Participant-level outcome: PSD (P-SIM) response for scaling at Week 16
To evaluate the efficacy of bimekizumab compared with placebo on the change in psoriatic scalp disease in study participants with scalp PSO at Baseline	
 Participant-level outcome: Scalp IGA 0/1 (clear or almost clear with at least a 2-category improvement from Baseline) response at Week 16 for study participants with scalp PSO at Baseline
To assess the effect of bimekizumab compared with placebo on QOL	
 Participant-level outcome: DLQI 0/1 response at Week 16
To evaluate the effect of bimekizumab compared with placebo on percent change from Baseline in BSA affected by PSO	
 Participant-level outcome: Percent change from Baseline in BSA affected by PSO at Week 16
To evaluate the safety of bimekizumab	
 Incidence of TEAEs throughout the study Incidence of TE-SAEs throughout the study Incidence of TEAEs leading to permanent discontinuation of IMP throughout the study

Objectives	Endpoints
To assess the effect of bimekizumab on depression occurrence or worsening	
 • Change from Baseline in PHQ-9 at Week 16
Tertiary	
To evaluate the PK of bimekizumab in study participants with moderate to severe PSO	
 • Plasma bimekizumab concentrations over the study duration
To evaluate the immunogenicity of bimekizumab	
 • Anti-bimekizumab antibody status over the study duration
To assess the efficacy of bimekizumab compared with placebo over time	
 • PASI75 response over time • PASI90 response over time • PASI100 response over time • Absolute and percent change from Baseline in PASI score over time • Percentage of study participants with absolute PASI score ≤ 1, ≤ 2, ≤ 3, and ≤ 5 over time • Time to PASI50, PASI75, PASI90, and PASI100 response • IGA 0/1 response (with at least 2-category improvement from Baseline) over time • IGA 0 response (with at least 2-category improvement from Baseline) over time • Scalp-specific IGA (scalp IGA) 0/1 response (clear or almost clear with at least 2-category improvement from Baseline for participants with scalp PSO at Baseline) over time • Percentage of study participants with absolute BSA affected by PSO=0%, $\leq 1\%$, $\leq 3\%$ and $\leq 5\%$ over time • Percentage of study participants achieving a DLQI Total Score of 0 or 1 over time • Change from Baseline in DLQI Total Score over time • PSD (P-SIM) response rates over time • Change from Baseline in PSD (P-SIM) scores over time
To further evaluate the safety of bimekizumab compared with placebo over time	
 • Selected safety topics of interest TEAEs • Change from Baseline in laboratory variables (hematology and biochemistry) • Incidence of markedly abnormal laboratory values • Change from Baseline in vital signs • Incidence of markedly abnormal vital signs

Objectives	Endpoints
	
 • Change from Baseline in ECG parameters • ECG outliers • Change from Baseline in PHQ-9 • Incidence of PHQ-9 scores ≥ 15 and ≥ 20 • Incidence of suicidal ideation, suicidal behavior, or self-injurious behavior without suicidal intent (from C-SSRS)

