14. Study participant has a known hypersensitivity to any excipients of bimekizumab.
15. Study participant has any other condition, including medical or psychiatric, which, in the Investigator's judgment, would make the study participant unsuitable for inclusion in the study.

Prior/concomitant therapy

16. Study participant has received any live (includes attenuated) vaccination within the 8 weeks prior to the Baseline visit (eg, inactivated influenza and pneumococcal vaccines are allowed but nasal influenza vaccination is not permitted). Live vaccines are not allowed during the study, including the SFU Period (20 weeks after the final dose of IMP).

Administration of any other type of vaccine that is not a live or inactivated vaccine must be discussed with the study Medical Monitor or UCB Study Physician.

17. Study participant has received Bacillus Calmette-Guerin vaccinations within 1 year prior to the Baseline visit.
18. Study participant has had major surgery (including joint surgery) within the 3 months prior to the Baseline Visit or has planned major surgery within the duration of the study.
19. Study participant is taking or has taken prohibited PSO medications (Section 6.5.2) without meeting the mandatory washout period relative to the Baseline Visit.

Prior/concurrent clinical study experience

20. Study participant previously participated in a bimekizumab clinical study and received at least 1 dose of the IMP (including placebo).
21. Study participant previously participated in another study of a medication (systemic) under investigation within the 12 weeks or at least 5 half-lives prior to the Screening Visit, whichever is greater, or is currently participating in another study of a medication (systemic) under investigation.
22. Study participant previously participated in another study of a topical medication under investigation within the 4 weeks prior to the Screening Visit, or is currently participating in another study of a topical medication under investigation.
23. Study participant previously participated in another study of a medical device under investigation within the 4 weeks prior to the Screening Visit, or is currently participating in another study of a medical device under investigation.

Diagnostic assessments

24. Study participant has laboratory abnormalities at Screening, including any of the following:

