9.4.1.3 Hematology/biochemistry

Treatment-emergent markedly abnormal (TEMA) laboratory values are defined as those that have an assessment date on or following first dose of IMP.

Laboratory assessments will be analyzed by visit. Absolute values and change from Baseline in each laboratory parameter will be presented descriptively for each treatment group. The incidence rate of TEMA laboratory values at the parameter level will also be presented descriptively for each treatment group. Definitions for markedly abnormal laboratory values will be provided in the SAP.

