# 5.6.3.1.1 Laboratory values over time

For tables where data are summarized by visit, unscheduled and repeat visits will not be summarized, but these data will be included in listings. For tables where multiple measurements over a period of time are considered (as in shift tables), unscheduled and repeat visits will be considered as long as they were collected in the period being summarized. All summaries will be presented in International System of Units and will be based on observed case values. In the case where laboratory values are below the LLQ, then these will be set to the midpoint between 0 and the lower limit of quantification for the purpose of summarizing the data.

The following summaries will be presented for data collected during the Treatment Period, SFU data will be included in listings only (unless otherwise specified).

- A summary of the absolute and change from Baseline values in each laboratory variable by treatment group and visit.
- A summary of the number and percentage of study participants experiencing markedly abnormal values at any time while on treatment (assessment on or following the first dose

of study treatment through to the end of the time at risk (see section 5.6.1)) by laboratory variable and treatment group

- A summary of the number and percentage of study participants with a given CTCAE grade (0,1,2,3, or 4) based on minimum/maximum post-baseline value by laboratory variable and treatment group
- A shift table of the number and percentage of study participants experiencing CTCAE grade 0,1,2,3, or 4 values (as applicable) at Baseline to maximum post-Baseline CTCAE grade, by laboratory variable and treatment group
- A figure presenting neutrophil CTCAE grade over time for study participants with at least one markedly abnormal neutrophil value (Grade 3 or above).
- Spaghetti plots presenting ALT values over time for study participants with at least one markedly abnormal ALT value (Grade 3 or above) (Including SFU).
- Spaghetti plots presenting AST values over time for study participants with at least one markedly abnormal AST value (Grade 3 or above) (Including SFU).
- A by-study participant listing of all laboratory data (including urinalysis) will be provided. This listing will be presented by treatment group and will include: center, subject identifier, age, sex, race, weight, visit, laboratory variable, result (with abnormal values flagged as "L" or "H" accordingly) and unit.

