#### Potentially Clinically Significant Criteria for Safety Endpoints 6.1.7

#### 6.1.7.1 Markedly abnormality criteria for laboratory data

Markedly abnormal values are defined as those with a severity of Grade 3 and above based on the common terminology criteria for adverse events (CTCAE) criteria (U.S. Department of Health and Human Services 2017). Definitions of markedly abnormal values using the Grade 3 cut points are given in the tables below for age ranges of  $\geq 17$  years (Table 10 for markedly abnormal hematology values, Table 11 for markedly abnormal biochemistry values, and Table 12 for markedly abnormal liver function test values). Tables summarizing markedly abnormal values should include a summary (counts and percentages) of markedly abnormal labs observed at any time while on treatment (i.e., treatment-emergent markedly abnormal [TEMA]). For this summary, Baseline values are not considered. The laboratory results classified as Grade 3 or Grade 4 will be summarized and listed separately.

Parameter	Co	nventional	s s	Abnormal	
name	Unit	Criteria	Unit	Criteria	Designation
Hemoglobin	/ 17	<8.0+	/ T	<8.0	AL
	g/dL	>4.0 above ULN	g/L	>4.0 above ULN	AH
Lymphocytes		<0.5	109/J	<0.5	AL
Absolute	10 ⁻⁷ L	>20.0	10 ² /L	>20.0	AH
Neutrophils Absolute	10 ⁹ /L	<1.0	10 ⁹ /L	<1.0	AL
Platelets	10 ⁹ /L	<50	10 ⁹ /L	<50	AL
WBC/Leukocytes	10 ⁹ /L	<2.0	10 ⁹ /L	<2.0	AL
y		>100		>100	AH

normal Hematology Values
n

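### Laboratory values are called treatment-emergent by sampling date alone, so a Grade 3 or higher value already present at Baseline that persists is counted as emergent

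*Protocol*

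**What the plan says.** Protocol Section 3 places "Incidence of markedly abnormal laboratory values" under the tertiary objective of further evaluating safety against placebo over time. That line does not use the term treatment-emergent.

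The term enters in Protocol 9.4.1.3: "Treatment-emergent markedly abnormal (TEMA) laboratory values are defined as those that have an assessment date on or following first dose of IMP". The section continues: "The incidence rate of TEMA laboratory values at the parameter level will also be presented descriptively for each treatment group".

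SAP 5.6.3.1.1 plans the number and percentage of participants with "markedly abnormal values at any time while on treatment (assessment on or following the first dose", with the window running on to the end of the time at risk. SAP 6.1.7.1 sets the limit at CTCAE Grade 3 or above (Tables 10 to 12), gives this on-treatment count the TEMA label, and adds: "For this summary, Baseline values are not considered".

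Three other parts of the plan bear on the point:

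- **Entry.** Criterion 24 of Protocol 5.2 ("Study participant has laboratory abnormalities at Screening, including any of the following") gives numeric limits for ALT, AST, ALP, total bilirubin, WBC, neutrophils, lymphocytes and hemoglobin. It also has an investigator-judgment clause for other abnormalities. Criterion 8 excludes uncontrolled or unstable systemic disease, including renal, liver and metabolic disease.
- **Other displays.** SAP 5.6.3.1.1 also plans change from Baseline by visit, a shift table from Baseline grade to worst post-Baseline grade, and a listing of all laboratory data. SAP 6.1.7.1 adds separate listing of Grade 3 and Grade 4 results.
- **Baseline.** SAP 5.1.1.1.5 takes the latest value on or before the first dosing day, and falls back on Screening if Baseline is missing.

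**The concern.** For an adverse event, the start date identifies onset, so a date rule is a sensible definition of treatment-emergent. For a laboratory value, the assessment date shows only when blood was drawn. Carried over to laboratory data, the date rule no longer separates new abnormalities from old ones.

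There is some reason to expect old ones. Protocol 2.2 says that metabolic syndrome, renal disease and diabetes are more common in psoriasis, and Protocol Table 10-1 specifies nonfasting glucose. That is background on comorbidity, not evidence of Grade 3 values in screened participants.

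At stake is whether a rate meant to compare safety with placebo mixes pre-existing disease with new toxicity. With planned arms of 30 and 15, a single participant visibly moves a rate, and randomization balances such cases only in expectation.

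**Working it through.** The documents state no figure for this endpoint, so there is nothing to reproduce. The check is textual, followed by simple arithmetic on the planned arm sizes.

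**1. How the plan treats Baseline elsewhere**

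| Item | Source | Baseline condition |
|---|---|---|
| Markedly abnormal blood pressure | SAP Table 13 | Yes: limit plus a change from Baseline |
| Treatment-emergent antidrug antibodies | SAP 5.7.1.4, Categories 2 and 5 | Yes: negative or missing at Baseline then positive, or boosted titer |
| QTcF outliers | SAP 5.6.3.3 | Absolute limits, with increases from Baseline also tabulated |
| PHQ-9 of at least 15 or 20 | SAP 5.6.3.6 | None, and not called treatment-emergent |
| Laboratory TEMA | Protocol 9.4.1.3, SAP 6.1.7.1 | None, but called treatment-emergent |

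**2. The SAP sentence has two readings.** "Baseline values are not considered" may mean that the Baseline record is not itself counted, or that Baseline status is ignored. The first is a useful clarification, because a Baseline sample can carry the date of first dose. Under both readings, a Grade 3 value that persists to a post-dose sample is counted as emergent. One that resolves before the next sample is not counted under the SAP.

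**3. Which parameters are exposed**

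| Parameter | Excluded at Screening | Markedly abnormal |
|---|---|---|
| ALT, AST, ALP | ≥3×ULN | >5×ULN |
| Total bilirubin | >ULN (≥1.5×ULN in Gilbert's syndrome) | >3×ULN |
| WBC (10⁹/L) | <3.00 | <2.0 |
| Neutrophils (10⁹/L) | <1.5 | <1.0 |
| Lymphocytes (10⁹/L) | <0.5 | <0.5 |
| Hemoglobin (g/dL) | <8.5 | <8.0 |

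For these parameters and directions, carry-over is unlikely. Glucose (>250 mg/dL), GGT (>5×ULN), triglycerides (>500 mg/dL), cholesterol (>400 mg/dL), creatinine, electrolytes and platelets have a TEMA limit but no numeric entry limit.

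**4. What the shift table can separate.** SAP Tables 14 and 15 grade triglycerides, cholesterol, creatinine, sodium, potassium, calcium and platelets. They give no grades for glucose or GGT.

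**5. Size per case.** One carried-over participant adds 1/30 = 3.3 points on bimekizumab or 1/15 = 6.7 points on placebo to that parameter's rate. As an example with assumed counts, take 30 bimekizumab participants, two at Grade 3 at Baseline and still so after dosing, and one new case. The present rule gives 3/30 = 10.0%. A rule with a Baseline condition gives 1/30 = 3.3%, or 1/28 = 3.6% among those not already beyond the limit.

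**6. How likely a candidate is.** Let p be the proportion of participants with a Grade 3 or higher Baseline value in any parameter without an entry limit. The documents give no p, so the values below are assumptions. The expected number is n × p, and the chance of at least one is 1 − (1 − p)ⁿ.

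| p | Expected, 30 / 15 | At least one of 30 | At least one of 15 | At least one of 45 |
|---|---|---|---|---|
| 1% | 0.3 / 0.15 | 26% | 14% | 36% |
| 2% | 0.6 / 0.30 | 46% | 26% | 60% |
| 5% | 1.5 / 0.75 | 79% | 54% | 90% |

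For a given p, these are upper bounds on miscounting, because the value must also exceed the limit in a post-dose sample. They pool parameters, and the last column also pools arms, whereas the plan reports by parameter and arm.

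**The case against.** The strongest reply is that the planned count matches the endpoint as Section 3 words it, so the fault is only a label. Absolute limits are also the plan's practice for PHQ-9 and, in part, QTcF. With about 45 participants, the listings show every pre-existing case, and the shift table does so for most exposed parameters. Investigators can exclude relevant abnormalities under criteria 8 and 24. The endpoint is tertiary, descriptive and untested, and a one-participant difference between arms of 30 and 15 means little under any definition.

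Much of this stands and limits the weight. Even the glucose and GGT gap is not certain. Tables 14 and 15 also omit ALT and AST, yet SAP 5.6.3.1.1 plots both at Grade 3 or above, so absence from those tables does not prove that GGT is left out of the shift table.

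The reply does not remove the point. The TEMA label is the stated definition in Protocol 9.4.1.3 and is repeated in SAP 6.1.7.1. The judgment-based exclusions set no threshold. The shift table and listings let a careful reader work around the headline rate, but they do not correct it.

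**Conclusion.** The point holds as a definitional fault of limited weight. A persisting Grade 3 or higher Baseline value is reported as treatment-emergent, at 3.3 points per case on bimekizumab and 6.7 on placebo for the parameter concerned. These figures assume full planned arms as denominators. The 36% to 90% range further assumes a 1% to 5% prevalence and counts every Baseline case as persisting.

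A reader might go further in four ways that the documents do not support:

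- That the Section 3 endpoint is itself wrong. It does not say treatment-emergent; the fault lies in the later definitions.
- That the SAP deliberately disregards Baseline status. Its sentence may only keep the Baseline record out of the count.
- That entry criteria and other displays give no protection. The numeric limits, the judgment clauses, the shift table and the listings all reduce the problem.
- That a between-arm safety conclusion will be distorted. No test is planned, and no Baseline prevalence is given from which to show distortion in any reported row.

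It is still worth correcting, because the stated rule does not do what its name says and the Baseline data are already collected.

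**What to change.** In SAP 6.1.7.1 and 5.6.3.1.1, and in Protocol 9.4.1.3, define TEMA as a value after the first dose beyond the markedly abnormal limit, in a participant whose Baseline value for that parameter and direction was not beyond it. Add a rise from Grade 3 at Baseline to Grade 4 only where the SAP defines both grades. That limb cannot be applied to glucose or GGT, which have a single cut point in each direction specified and no grade table.

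Use as denominator the participants with a Baseline value and at least one post-Baseline value for the parameter. This also settles how a missing Baseline is handled; few should be lost, since Screening already serves as the fallback.

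Keep the present count as a second row labelled 'any post-Baseline markedly abnormal value', so that no information is lost.

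The cost is a short text change in each document, one programming condition on data already collected, and slightly smaller denominators.
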